8.2 Secondary Objectives

- To assess PROs, treatment adherence and treatment satisfaction during treatment with cladribine tablets
- To assess treatment patterns (MS treatment prior to transition to cladribine tablets since MS diagnosis, concomitant treatment for MS during the last 2 years prior to initiation of cladribine tablets (or since MS diagnosis, if diagnosis <24 months), follow-up treatment in case of discontinuation of cladribine tablets); and in particular, to assess the clinical and demographic characteristics related to the sequential use of ocrelizumab and cladribine
- To estimate the ARR over the 24-month period prior to initiation of cladribine tablets (or since MS diagnosis, if diagnosis <24 months)
- To collect all serious adverse events (SAEs), adverse drug reactions (ADRs), adverse events of special interest (AESI) and special situations during and following treatment with cladribine tablets over a 24-month period

CCI

9 Research Methods

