9.1.2.2 Secondary

- Baseline scores and change in scores from baseline to Months 6, 12 and 24 for the following PROs (collected via electronic PRO [ePRO] at the practice or at the patient's home using computer's URL or device application; validated Spanish translations are available for all PROs, except for the Patient Determined Disease Steps (PDDS) scale for which a translation is used that has not been linguistically validated):
 - 14-Item Treatment Satisfaction Questionnaire for Medication (TSQM). TSQM-14 is an instrument to assess patient's satisfaction with medication, providing scores on 4 scales: side effects, effectiveness, convenience, and global satisfaction.
 - 36-Item Short Form Health Survey (SF-36). SF-36 is a self-administered, generic health status questionnaire consisting of 36 questions that measure 8 health concepts: physical functioning, role limitations due to physical problems, bodily pain, general health perception, vitality, social functioning, role limitations due to emotional problems and mental health.
 - Modified Fatigue Impact Scale – 5-item version (MFIS-5). MFIS-5 is a modified form of the Fatigue Impact Scale that consists of 5 questions that assess the impact of fatigue on physical, cognitive, and psychosocial functioning, with 5 response levels ranging from 0 ("Never") to 4 ("Almost always"). Total scores range from 0 to 20, with higher scores representing a greater impact of fatigue.
 - Beck-Depression Inventory-Fast Screen (BDI-FS) [7 items]. The 7 items BDI-FS is a self-report inventory for measuring the severity of depression on a 7-item scale.
 - Work Productivity Activity Impairment – MS (WPAI-MS) [6 items]. The WPAI-MS questionnaire is a validated instrument to measure impairments in work and activities. The WPAI yields 4 types of scores: 1. Absenteeism (work time missed); 2. Presenteeism (impairment at work / reduced on-the-job effectiveness); 3. Work productivity loss (overall work impairment / absenteeism plus presenteeism); 4. Activity Impairment. WPAI outcomes are expressed as impairment percentages, with higher numbers indicating greater impairment and less productivity.

- PDDS scale. The PDDS is a patient-reported scale to assess the disability status in patients with MS and it focuses mainly on how patients walk. A higher score represents a higher level of disability. Scores on the PDDS range from 0 (normal) to 8 (bedridden).

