9.2.2 Definition of Study Cohorts and Description of Treatments

The study will have a single primary cohort that consists of all patients enrolled in the study who received at least 1 dose of cladribine tablets. Additionally, a sub-cohort of approximately 100 patients that directly switched from ocrelizumab to cladribine tablets will be prospectively enrolled. All treatment and other medical decisions will be made by the investigator, with no directives mandated by this study protocol.

All study patients are anticipated to receive marketed cladribine tablets as per investigator discretion and as per US approved label: 3.5 mg/kg body weight over 2 years, administered as 1 treatment course of 1.75 mg/kg per year. Each treatment course consists of 2 treatment weeks, 1 at the beginning of the first month and 1 at the beginning of the second month of the respective year. Each treatment week consists of 4 or 5 days on which a patient receives 10 mg or 20 mg (1 or 2 tablets) as a single daily dose, depending on body weight. Since prescribing is determined by the investigator as per standard of care and according to the USPI, the benefits and risks to patients in being in the study are not different than the benefits and risks to patients taking cladribine tablets as per standard of care and according to the USPI in the general population.

Following completion of the 2 treatment courses, do not administer additional cladribine tablet treatment during the next 2 years, as stated in the USPI.

As per USPI, ALC values need to be normal at the initiation of cladribine tablets in Year 1, and ALC results need to indicate ≥ 800 cells per microliter at the start of the Year 2 treatment course. If necessary, the Year 2 treatment course should be delayed for up to 6 months to allow for recovery of lymphocytes to ≥ 800 cells per microliter. If this recovery takes more than 6 months, the patient should not receive further treatment with cladribine tablets.

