9.2.3 Observation Period

Each patient will be followed from the date of first dose of cladribine tablets until loss to follow-up, withdrawal of consent, death, or the end of the data collection period, whichever comes first. Patients will be followed for 24 months from first dose and up to 30 months for those patients who may require a delay of initiation of Year 2 treatment for up to 6 months due to low lymphocyte counts. Follow-up will continue regardless of cladribine tablets discontinuation.

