## 5 Objectives and Endpoints

Objectives	Endpoints (Outcome Measures)	Endpoints (Outcome Measures) Timeframe	IAP Section
Primary			
To estimate the annualized relapse rate (ARR) over a 24-month period in patients with Relapsing form of Multiple Sclerosis (RMS), including relapsing-remitting multiple sclerosis (RRMS) and active secondary progressive multiple sclerosis (aSPMS) who are treated with cladribine tablets in a real-world setting and after suboptimal response to any oral or infusion Disease-Modifying Drug (DMD) approved in the United States (US) for RMS	ARR over 24 months of treatment with cladribine tablets (prospectively collected data)	24-month period from first dose of cladribine tablets (or 30 months if Year 2 treatment is delayed)	Section 14.1
Secondary	
To assess Patient-Reported Outcomes (PROs), treatment adherence, and treatment satisfaction during treatment with cladribine tablets
 
Baseline scores, scores at the timepoints, and change in scores from Baseline to timepoints (Month 6, 12, and 24) for the following PROs (collected via electronic PRO [ePRO] at the practice or at the patient's home):
 

• 14-Item Treatment Satisfaction Questionnaire for Medication (TSQM)

• 36-Item Short Form Health Survey (SF-36)

• Modified Fatigue Impact Scale – 5-item version (MFIS-5)

• Beck-Depression Inventory – Fast Screen (BDI-FS) (7 items)

• Work Productivity Activity Impairment – Multiple Sclerosis (WPAI-MS) (6 items)

	24-month period from enrollment	Section 16.3 and Section 16.4

Objectives	Endpoints (Outcome Measures)	Endpoints (Outcome Measures) Timeframe	IAP Section
	
 
Patient Determined Disease Steps (PDDS) scale
 
 
Treatment adherence based on modified versions of the MS-TAQ; data to be collected via ePRO at Baseline (modified for once- or twice-daily oral dosing to assess adherence during last previous oral DMD treatment, or modified for infusion dosing to assess adherence to last previous infusion DMD treatment, only baseline scores) and at the end of Months 1, 2, 13, and 14 (modified for cladribine tablets, only scores at the different time points)
	Timepoints for TSQM, SF-36, MFIS-5, BDI-FS, WPAI-MS, and PDDS: Baseline, Months 6, 12, and 24 (or 30 months if Year 2 treatment is delayed) Adherence assessment timepoints: Baseline (adherence to previous DMD), Months 1, 2, 13, and 14 (adherence to cladribine)	

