### 16.3

### Patient-Reported Outcome

Analysis (Analysis Population)	Derivation	Statistical Analysis Methods	Missing Data Handling
Secondary Endpoints: ePROs			
Secondary (FAS)	Scores collected at Baseline and at Months 6, 12, and 24 for the following PROs (TSQM, SF-36, MFIS-5, BDI-FS, WPAI-MS)	Baseline scores and change from baseline scores will be summarized descriptively	See description in section 16.3
	Scores collected at Baseline and at Months 6, 12, and 24 for PDDS	Baseline scores and change from baseline scores will be summarized descriptively	See description in section 16.3

BDI-FS: Beck-Depression Inventory-Fast Screen; ePROs: electronic patient-reported outcomes; FAS: Full Analysis Set; MFIS-5: Modified Fatigue Impact Scale – 5-Item Version; PDDS: Patient Determined Disease Steps; PRO: Patient-reported outcome; SF-36: 36-Item Short Form Health Survey; TSQM: Treatment Satisfaction Questionnaire for Medication; WPAI-MS: Work Productivity Activity Impairment-Multiple Sclerosis

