### TSQM

TSQM-1.4 is an instrument to assess patient satisfaction with medications, providing scores on 4 scales: side effects, effectiveness, convenience, and global satisfaction. With the exception of item (i.e., question) 4 (presence of side effects; yes or no), all items have 5 or 7 responses, scored

from 1 (least satisfied) to 5 or 7 (most satisfied). Higher scores indicate higher satisfaction. Scores for each domain are computed by adding the TSQM items in each domain and then transforming the composite score into a value ranging from 0 to 100. Of note, a score can be computed for a domain only if no more than one item is missing from that domain. The calculations specific to each domain are presented in detail below.

*Global Satisfaction*

$([(\text{Sum (Item 12 to Item 14)}) - 3] \text{ divided by } 14) * 100$

If Item 12 or 13 is missing:

$([(\text{Sum (the 2 completed items)}) - 2] \text{ divided by } 10) * 100$

If Item 14 is missing:

$([(\text{Sum (Item 12 and Item 13)}) - 2] \text{ divided by } 8) * 100$

*Effectiveness*

$([(\text{Item 1} + \text{Item 2} + \text{Item 3}) - 3] \text{ divided by } 18) * 100$

If one item is missing:

$([\text{Sum (the 2 completed items)}) - 2] \text{ divided by } 12) * 100$

*Side Effects*

If Question 4 is answered “No,” then score = 100

Else

$([\text{Sum (Item 5 to Item 8)} - 4] \text{ divided by } 16) * 100$

If one item is missing:

$([(\text{Sum (the 3 completed items)}) - 3] \text{ divided by } 12) * 100$

*Convenience*

$([\text{Sum (Item 9 to Item 11)} - 3] \text{ divided by } 18) * 100$

If one item is missing:

$([(\text{Sum (the 2 completed items)}) - 2] \text{ divided by } 12) * 100$

The 14 items are listed in the Appendices.

Each derived score will be summarized descriptively as a continuous variable.

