## 18                    Appendices

### TSQM items

1. How satisfied or dissatisfied are you with the ability of the medication to prevent or treat your condition?  
(Score 1 to 7)
2. How satisfied or dissatisfied are you with the way the medication relieves your symptoms?  
(Score 1 to 7)
3. How satisfied or dissatisfied are you with the amount of time it takes the medication to start working?  
(Score 1 to 7)
4. As a result of taking this medication, do you currently experience any side effects at all?

(Score 0[No] or 1[Yes])

5. How bothersome are the side effects of the medication you take to treat your condition?

(Score 1 to 5)

6. To what extent do the side effects interfere with your physical health and ability to function (i.e., strength, energy level, etc.)?

(Score 1 to 5)

7. To what extent do the side effects interfere with your mental function (i.e., ability to think clearly, stay awake, etc.)?

(Score 1 to 5)

8. To what degree have medication side effects affected your overall satisfaction with the medication?

(Score 1 to 5)

9. How easy or difficult is it to use the medication in its current form?

(Score 1 to 7)

10. How easy or difficult is it to plan when you will use the medication each time?

(Score 1 to 7)

11. How convenient or inconvenient is it to take the medication as instructed?

(Score 1 to 7)

12. Overall, how confident are you that taking this medication is a good thing for you?

(Score 1 to 5)

13. How certain are you that the good things about your medication outweigh the bad things?

(Score 1 to 5)

14. Taking all things into account, how satisfied or dissatisfied are you with this medication?

(Score 1 to 7)

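### The TSQM summary under the cladribine objective can include ratings of other drugs, and its side-effects score misses effects that resolved after the treatment weeks

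*SAP*

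**What the plan says.** Protocol 8.2 states the objective as "To assess PROs, treatment adherence and treatment satisfaction during treatment with cladribine tablets", and SAP 5 repeats it. The endpoint in Protocol 9.1.2.2 is "Baseline scores and change in scores from baseline to Months 6, 12 and 24 for the following PROs", and the 14-item TSQM heads that list. SAP 16.3 analyses it in the FAS: "Baseline scores and change from baseline scores will be summarized descriptively".

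Stopping cladribine does not end participation. Protocol 9.2.3 says "Follow-up will continue regardless of cladribine tablets discontinuation", and Protocol 9.3 logs other MS DMDs taken during the study with their start and stop dates. SAP 8.2 defines a subgroup of patients who do not complete treatment, but applies subgroup analyses to the primary endpoint only.

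The TSQM items in SAP 18 refer to a medication without naming it. Item 4 reads "As a result of taking this medication, do you currently experience any side effects at all". Under the scoring rules in SAP 16.3, if the answer is No, "then score = 100"; otherwise the domain is computed from items 5 to 8.

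On dosing, Protocol 9.2.2 says "Each treatment course consists of 2 treatment weeks, 1 at the beginning of the first month and 1 at the beginning of the second month", with 4 or 5 dosing days per treatment week. A footnote to Protocol Table 1 places the baseline questionnaires before the first tablet.

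**The concern.** Treatment satisfaction is a named secondary objective, tied to time on cladribine. Three features loosen that tie.

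- **After a switch.** A patient who has stopped cladribine and begun another MS DMD answers a form about an unnamed medication. The score may describe the new drug, yet it enters the same mean.
- **Side effects.** Cladribine is taken in a few short weeks, while the TSQM is completed months later and item 4 asks about the present. A patient who felt unwell in the treatment weeks and then recovered can truthfully answer No and receive the maximum.
- **Baseline.** The form cannot rate cladribine. Protocol 9.2.4 expects the previous DMD to be discontinued first in at least some patients, so the baseline answer may also come after that drug was stopped.

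A reader given only domain means and changes could not separate experience with cladribine from switching and from the dosing calendar.

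**Working it through.** **1. Attribution: TSQM against MS-TAQ.** SAP 16.4 and 18 give the MS-TAQ three versions: previous oral DMD, previous infused DMD, and cladribine. No such versions are described for the TSQM, and SAP 16.3 has no rule for scores given after another DMD starts. The data for such a rule exist. DMD start dates are in the log (Protocol 9.3), and the TSQM windows in SAP 9 are counted from Day 1, so form dates must be available.

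**2. Side-effects scoring (SAP 16.3).** With a Yes to item 4 and all four items answered, score = (sum of items 5–8 − 4) / 16 × 100. Items all at 1, 2, 3, 4 or 5 give 0, 25, 50, 75 or 100. The plan's fixed value of 100 after a No therefore equals the best possible answer on items 5–8.

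**3. Time from last tablet to form.** Inputs: 1 month = 30.4375 days (SAP 9), 4 or 5 dosing days per week (Protocol 9.2.2), and windows of ±30 days (SAP 9). The Year 2 course is taken to start at Day 365.25 plus any delay.

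- Last Year 1 tablet: 30.4375 + 4 = Day 34.4 (Day 35.4 with 5 days).
- Month 6: (182.6 − 34.4) / 30.4375 = 4.9 months; 3.9 to 5.9 across the window.
- Month 12, Year 2 course not yet started: (365.25 − 34.4) / 30.4375 = 10.9 months; 9.9 to 11.9 across the window.
- Month 24, no delay, last tablet Day 399.7: (730.5 − 399.7) / 30.4375 = 10.9 months; 9.9 to 11.9 across the window.
- Month 24, 3-month delay, last tablet Day 491.0: 7.9 months; 6.9 to 8.9 across the window.
- Month 24, 6-month delay, last tablet Day 582.3: 4.9 months; 3.9 to 5.9 across the window.

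Five dosing days shorten a gap by at most about 0.1 month. There are two exceptions to the range of about 4 to 12 months. The Month 12 window runs from Day 335 to Day 395, so a late form can fall in or after the first Year 2 treatment week. A patient who never takes the Year 2 course is further out at Month 24: (730.5 − 34.4) / 30.4375 = 22.9 months.

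**4. Possible size, on assumed values only.** The documents give no switching rate, no item 4 frequencies and no TSQM standard deviation.

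- Switching: shift in the mean = share rating another drug × difference in rating. For 5% and 10 points, 0.05 × 10 = 0.5; for 20% and 40 points, 0.20 × 40 = 8.
- Side-effects domain: mean = 100 − p × (100 − m), where p is the share answering Yes and m their mean score. If p falls from 0.5 at baseline to 0.1 at follow-up with m fixed, the change is 0.4 × (100 − m): 24, 16 or 8 points for m = 40, 60 or 80. If p and m do not change, the change is zero.

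**The case against.** The strongest reply is that experience around dosing is measured elsewhere. Item 7 of the cladribine MS-TAQ, sent at Months 1, 2, 13 and 14, names cladribine, asks about satisfaction in the treatment week, and serves the same objective. The adverse-event tables (SAP 15.1), lymphopenia grades (SAP 15.3) and reasons for discontinuation (SAP 13) cover tolerability. This stands: the study is not blind to events around dosing, and the gap concerns what the TSQM itself can show.

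Second, the value 100 follows a No, not the passage of time. A patient with lasting or late effects is scored from items 5–8. This stands too.

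Third, if many patients also answer No at baseline, both ends lie near the ceiling and the change is close to zero. That is correct, so the direction of any distortion in the change score cannot be predicted. The change still does not measure how cladribine was tolerated during treatment.

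Fourth, SAP 18 prints an item list, not the ePRO screens or instructions. Patients may have been told which drug to rate. That cannot be excluded, but neither document says so.

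Finally, the summaries are descriptive, and Protocol 9.9 warns in general terms that varied treatments may limit interpretation. That lowers the stakes, but it does not tell a reader which TSQM scores belong to which drug.

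**Conclusion.** The point holds as a matter of attribution and reporting. The TSQM summary under the cladribine objective includes patients who have started another MS DMD, with nothing to separate their ratings. The side-effects domain does not capture effects that resolved after the treatment weeks, because a No to item 4, plausible about 4 to 12 months after the last tablet, scores 100. Every change score sets a pre-cladribine rating against a later one.

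The size is not known from the documents. The 0.5 to 8 points for switching and the 8 to 24 points for the side-effects domain rest wholly on assumed shares and ratings, and the latter falls to zero if the Yes share and the score among Yes stay the same.

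A reader might infer that the delay alone drives the domain to 100, or that good tolerability will appear almost whatever happens. The documents support neither: the rule depends on the answer, its frequency is not given, and the MS-TAQ and safety tables report separately. Nor do the documents call the score satisfaction with cladribine. They speak of satisfaction during cladribine treatment, so that reading is fair but inferred.

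**What to change.** In SAP 16.3:

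- Base the main TSQM summary on assessments dated before the start of another MS DMD, using the DMD log. Show the all-visits summary and the post-switch scores separately.
- Beside the side-effects domain mean, report at each time point the proportion answering Yes to item 4 and the domain score among them.
- State that the baseline form rates the previous DMD, so change contrasts different drugs.
- Say that the domain is to be read together with item 7 of the cladribine MS-TAQ and the adverse-event tables.

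The cost is SAP wording, one extra table, and fewer TSQM records at Months 12 and 24 in the main summary. All the data are already collected.

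Two further changes may look attractive and should not be made. Adding the TSQM at Months 2 and 14 is no longer possible: last patient last visit was planned for 03-Jan-2025 and SAP version 4.0 is dated 23 Jan 2025. Withholding change scores from patients already off their previous DMD at baseline could remove much of the endpoint, because Protocol 9.2.4 anticipates that the previous drug is stopped first.

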## **HEALTH STATUS QUESTIONNAIRE (SF-36)**

This survey asks for your views about your health. This information will help keep track of how you feel and how well you are able to do your usual activities. Thank you for completing this survey!

For each of the following questions, please select the one response that best describes your answer.

Item Name	Question Text	Answer Text 1	Answer Text 2	Answer Text 3	Answer Text 4	Answer Text 5	Answer Text 6
	
 
• Your Health and Well-Being
 
						
	
 
• This survey asks for your views about your health. This information will help keep track of how you feel and how well you are able to do your usual activities. Thank you for completing this survey!
 
 
For each of the following questions, please select the one response that best describes your answer.
						
SF36v2_GH1	In general, would you say your health is:	Excellent	Very good	Good	Fair	Poor	
SF36v2_HT	Compared to one year ago , how would you rate your health in general now ?	Much better now than one year ago	Somewhat better now than one year ago	About the same as one year ago	Somewhat worse now than one year ago	Much worse now than one year ago	
	The following questions are about activities you might do during a typical day. Does your health now limit you in these activities? If so, how much?						
SF36v2_PF01	Does your health now limit you in vigorous activities , such as running, lifting heavy objects, participating in strenuous sports? If so, how much?	Yes, limited a lot	Yes, limited a little	No, not limited at all			
SF36v2_PF02	Does your health now limit you in moderate activities , such as moving a table, pushing a vacuum cleaner, bowling, or playing golf? If so, how much?	Yes, limited a lot	Yes, limited a little	No, not limited at all			
SF36v2_PF03	Does your health now limit you in lifting or carrying groceries? If so, how much?	Yes, limited a lot	Yes, limited a little	No, not limited at all			
SF36v2_PF04	Does your health now limit you in climbing several flights of stairs ? If so, how much?	Yes, limited a lot	Yes, limited a little	No, not limited at all			
SF36v2_PF05	Does your health now limit you in climbing one flight of stairs ? If so, how much?	Yes, limited a lot	Yes, limited a little	No, not limited at all			
SF36v2_PF06	Does your health now limit you in bending, kneeling, or stooping? If so, how much?	Yes, limited a lot	Yes, limited a little	No, not limited at all			
SF36v2_PF07	Does your health now limit you in walking more than a mile ? If so, how much?	Yes, limited a lot	Yes, limited a little	No, not limited at all			
SF36v2_PF08	Does your health now limit you in walking several hundred yards ? If so, how much?	Yes, limited a lot	Yes, limited a little	No, not limited at all			
SF36v2_PF09	Does your health now limit you in walking one hundred yards ? If so, how much?	Yes, limited a lot	Yes, limited a little	No, not limited at all			
SF36v2_PF10	Does your health now limit you in bathing or dressing yourself? If so, how much?	Yes, limited a lot	Yes, limited a little	No, not limited at all			

Item Name	Question Text	Answer Text 1	Answer Text 2	Answer Text 3	Answer Text 4	Answer Text 5	Answer Text 6
	During the past 4 weeks , how much of the time have you had any of the following problems with your work or other regular daily activities as a result of your physical health ?						
SF36v2_RP1	During the past 4 weeks , how much of the time have you cut down on the amount of time you spent on work or other activities as a result of your physical health ?	All of the time	Most of the time	Some of the time	A little of the time	None of the time	
SF36v2_RP2	During the past 4 weeks , how much of the time have you accomplished less than you would like as a result of your physical health ?	All of the time	Most of the time	Some of the time	A little of the time	None of the time	
SF36v2_RP3	During the past 4 weeks , how much of the time were you limited in the kind of work or other activities as a result of your physical health ?	All of the time	Most of the time	Some of the time	A little of the time	None of the time	
SF36v2_RP4	During the past 4 weeks , how much of the time have you had difficulty performing the work or other activities as a result of your physical health (for example, it took extra effort)?	All of the time	Most of the time	Some of the time	A little of the time	None of the time	
	During the past 4 weeks , how much of the time have you had any of the following problems with your work or other regular daily activities as a result of any emotional problems (such as feeling depressed or anxious)?						
SF36v2_RE1	During the past 4 weeks , how much of the time have you cut down on the amount of time you spent on work or other activities as a result of any emotional problems (such as feeling depressed or anxious)?	All of the time	Most of the time	Some of the time	A little of the time	None of the time	
SF36v2_RE2	During the past 4 weeks , how much of the time have you accomplished less than you would like as a result of any emotional problems (such as feeling depressed or anxious)?	All of the time	Most of the time	Some of the time	A little of the time	None of the time	
SF36v2_RE3	During the past 4 weeks , how much of the time have you done work or other activities less carefully than usual as a result of any emotional problems (such as feeling depressed or anxious)?	All of the time	Most of the time	Some of the time	A little of the time	None of the time	
SF36v2_SF1	During the past 4 weeks , to what extent has your physical health or emotional problems interfered with your normal social activities with family, friends, neighbors, or groups?	Not at all	Slightly	Moderately	Quite a bit	Extremely	
SF36v2_BP1	How much bodily pain have you had during the past 4 weeks ?	None	Very mild	Mild	Moderate	Severe	Very severe
SF36v2_BP2	During the past 4 weeks , how much did pain interfere with your normal work (including both work outside the home and housework)?	Not at all	A little bit	Moderately	Quite a bit	Extremely	
	These questions are about how you feel and how things have been with you during the past 4 weeks . For each question, please give the one answer that comes closest to the way you have been feeling.						

Item Name	Question Text	Answer Text 1	Answer Text 2	Answer Text 3	Answer Text 4	Answer Text 5	Answer Text 6
SF36v2_VT1	How much of the time during the past 4 weeks did you feel full of life?	All of the time	Most of the time	Some of the time	A little of the time	None of the time	
SF36v2_MH1	How much of the time during the past 4 weeks have you been very nervous?	All of the time	Most of the time	Some of the time	A little of the time	None of the time	
SF36v2_MH2	How much of the time during the past 4 weeks have you felt so down in the dumps that nothing could cheer you up?	All of the time	Most of the time	Some of the time	A little of the time	None of the time	
SF36v2_MH3	How much of the time during the past 4 weeks have you felt calm and peaceful?	All of the time	Most of the time	Some of the time	A little of the time	None of the time	
SF36v2_VT2	How much of the time during the past 4 weeks did you have a lot of energy?	All of the time	Most of the time	Some of the time	A little of the time	None of the time	
SF36v2_MH4	How much of the time during the past 4 weeks have you felt downhearted and depressed?	All of the time	Most of the time	Some of the time	A little of the time	None of the time	
SF36v2_VT3	How much of the time during the past 4 weeks did you feel worn out?	All of the time	Most of the time	Some of the time	A little of the time	None of the time	
SF36v2_MH5	How much of the time during the past 4 weeks have you been happy?	All of the time	Most of the time	Some of the time	A little of the time	None of the time	
SF36v2_VT4	How much of the time during the past 4 weeks did you feel tired?	All of the time	Most of the time	Some of the time	A little of the time	None of the time	
SF36v2_SF2	During the past 4 weeks , how much of the time has your physical health or emotional problems interfered with your social activities (like visiting with friends, relatives, etc.)?	All of the time	Most of the time	Some of the time	A little of the time	None of the time	
	How TRUE or FALSE is each of the following statements for you?						
SF36v2_GH2	I seem to get sick a little easier than other people.	Definitely true	Mostly true	Don't know	Mostly false	Definitely false	
SF36v2_GH3	I am as healthy as anybody I know.	Definitely true	Mostly true	Don't know	Mostly false	Definitely false	
SF36v2_GH4	I expect my health to get worse.	Definitely true	Mostly true	Don't know	Mostly false	Definitely false	
SF36v2_GH5	My health is excellent.	Definitely true	Mostly true	Don't know	Mostly false	Definitely false	
	SF-36v2® Health Survey © 1992, 2000, 2009 Medical Outcomes Trust and QualityMetric Incorporated. All rights reserved. SF-36® is a registered trademark of Medical Outcomes Trust. (SF-36v2® Health Survey Standard, United States (English))						

**MS-TAQ Modified version for once or twice daily oral dosing to assess adherence  
during last previous oral DMD treatment**

1.) Before enrolling in this study, what oral medication were you taking to treat your Multiple Sclerosis (MS)? (Check one)

Aubagio (teriflunomide)	
Gilenya (fingolimod)	
Tecfidera (dimethyl fumarate)	

2.) During the last 4 weeks (28 days) that you were taking this medication, how many days were you supposed to take this medication? (Check one)

Twice a day (58 times)	
Once a day (28 times)	
Other, please specify:	

3.) Did you miss or forget to take any doses of this medication during the last 4 weeks (28 days) that you were taking the medication? (Check one)

Yes	
No	

4.) How many doses did you miss or forget to take? (Complete blank)

